Investigating the effects of cuing medication availability on patient-controlled analgesia pump usage in pediatric patients: Results of a randomized controlled trial

NCT02456909

Date of Document: March 30, 2015

Study Protocol and Statistical Analysis Plan

Materials and Methods

This single-center, prospective, RCT was conducted at a large children's hospital in the Midwest. The study was approved by the hospital Institutional Review Board, and was registered at www.clinicaltrials.gov (ID: NCT02456909) by the principal investigators prior to study enrollment. Enrollment was April 2015 – August 2017.

Participants

Potential participants between the ages of 7 – 17 years, undergoing an orthopedic, abdominal or thoracic surgery for which PCA is routinely prescribed for post-operative pain management, were identified from the hospital surgery schedule. Eligible patients were opioid naïve, and patients and at least one parent were able to read and speak English. Exclusion criteria included 1) prior experience with PCA, 2) cognitive delay precluding independent use of the PCA button, or 3) pre-operative use of a daily anxiolytic or antidepressant medication.

Procedures

Recruitment and Randomization

Patients were approached immediately prior to surgery. After informed consent and assent were obtained, participants were randomized into either the control group or the experimental “light” group and were stratified by gender and surgical procedure (orthopedic, abdominal, or thoracic) in blocks of 4. The randomization scheme was created by a statistician on the research team using Windows version 6.0 of “rand.exe” (<http://block-stratified-randomization.software.informer.com>). Participants were enrolled by the clinical research coordinator, who used the scheme to assign participants to groups after consent. Recruitment continued until each group included 60 completed participants (defined as having completed at least 24 hours of PCA use and completed assessment of the primary outcome). Carefusion

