All outcomes were collected on post-operative days (PODs) 0-2, with the exception of state anxiety on POD 0, which was collected prior to surgery in the pre-op holding area. The research coordinator administered the STAI once on each POD, and also extracted all other data from the participant's electronic health record (EHR).

Demographics, anthropometrics, and treatment

Demographics (age, sex, race and ethnicity) and anthropometrics (height, weight, and BMI percentile) were extracted from the EHR. Benzodiazepine (lorazepam, diazepam), acetaminophen, ibuprofen, and ketorolac use and intraoperative methadone administration were also extracted from the EHR. These data were collapsed across PODs, and reported as presence/absence. Pre-existing chronic pain was also extracted from the EHR and reported as presence/absence.

Primary Outcome: Patient satisfaction with pain management

The primary outcome was the patient's response to a single question, focused specifically on satisfaction with pain management: "*How satisfied were you with your pain management (was your pain well controlled)?*," with 0 = "very dissatisfied" and 10 = "very satisfied". Participants answered additional questions to rule out factors that could potentially explain between-group similarities or differences in opioid consumption (e.g. Did you

understand how to use the pain pump?). These questions were completed independently by the patient within 24 hours of the end of the study period. Questions were developed by experts in pediatric pain management and were based on the study by Patak et al.¹

Secondary Outcomes

Opioid consumption and opioid-related side-effects

Data on opioid consumption and treatment of related side effects were extracted from the EHR. Total opioid consumed via PCA was calculated from all opioid delivered via the basal rate and via injections, and is reported in mg/kg/hr. Hydromorphone was converted to morphine equivalents by multiplying the total amount of hydromorphone consumed (mg) by 5.²

Data on side effects requiring treatment included nausea/vomiting, pruritus, over sedation (using the Children's Hospital of Wisconsin Sedation Scale,³ and respiratory depression. Treatment was coded as yes/no for each POD.

Pain intensity

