Pain scores: Pain scores were recorded from the time patients left the PACU until discontinuation of the PCA or through POD 2 (whichever came first) and were extracted from the EHR. Pain was assessed using the age appropriate, hospital approved pain scale. Children either used a 0-10 (0 = no pain, 10 = worst pain possible) numeric rating scale, or the 0-10 Faces Pain Scale-Revised [10].

PCA usage

The total number of hourly injections and attempts were extracted from the EHR.

State Anxiety

The Spielberger State-Trait Anxiety Inventory for Children (STAIC), state version, is a well-validated 20 item questionnaire used to assess anxiety about a current situation or impending event⁴. Each question begins with the stem “I feel...” and ends with 3 choices (e.g., “very calm,” “calm,” “not calm”). Respondents are instructed to consider “*how you feel right now.*” A total score is computed from a sum of the items, with scores ranging from 0 – 60. The STAIC was administered by the research coordinator once before surgery (POD 0) and once per day on POD 1 and POD 2. Elevated state anxiety was based on T-scores and was defined as ≥ 1 standard deviation above the mean.⁵

Power Analysis:

An *a priori* sample size calculation was based on the primary outcome. Rahman et al. examined patient satisfaction with pain relief for those randomized to pain management with PCA vs. intravenous boluses of analgesia titrated to patient comfort levels.⁶ Based on a 1-5 scale (1 = excellent, 5 = disappointing), the average pain relief rating for patients in the PCA group was significantly better at 2.0 (± 0.37) than the rating for patients in the control group at 3.0 (± 0.24). With a power of 80%, a type I error rate (alpha) of 0.05, and a two-tailed t test, 60 patients would have been needed in each group to detect a difference of at least 0.16 SD between the light and control groups.

Statistical Analysis

Modified intent-to-treat analyses included all randomized participants, with the exception of those who did not receive the allocated intervention, as shown in Figure 1. Means and standard deviations or median and interquartile range (IQR) when data were skewed, were used for continuous data, and categorical items were described using frequency statistics. A Chi-square test or a Fisher’s exact test was used to explore the relations between categorical variables, and bivariate correlations (Pearson correlation test) were used to explore correlations

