between continuous variables. Comparisons between intervention and control groups and between age groups [children (≤ 12 years) and adolescents (13-17 years)] were conducted using a Mann-Whitney test. Missing data were treated using listwise deletion, and assumed to be missing completely at random. A two-sided p-value <0.05 was used to define what was considered significant.

Multivariable analyses using a mixed model with random time were used to examine the effect of the intervention group and age group on two dependent variables (DV): 1) opioid consumption over time and, 2) injections:attempts ratio over time. The independent covariates (IV) considered were pain scores, methadone use and the interaction between methadone use and intervention group, age group, intervention group, and the interaction between age group and intervention group. A backward model selection procedure was used, with a p-value <0.05 as a criterion to keep the variable in the multivariable model. Based on this criterion, the interaction between intraoperative methadone and intervention group was dropped from the model. The DV opioid consumption was transformed using square root to satisfy model assumptions. The parameters were estimated using Maximum likelihood, and unstructured covariance structure was used for repeated measurements. The mixed model with random effects allows for missing data, under the assumption that data were missing at random. Statistical analyses were calculated using SPSS 24 (IBM SPSS Inc., Chicago, IL) and SAS 9.4 software (SAS Institute Inc., Cary, NC).

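### The power statement claims 80% power for 0.16 SD with 60 per group; 60 per group detects about 0.52 SD, and power at 0.16 SD is about 14%

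*Combined protocol and SAP*

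**What the plan says.** All references are to the combined protocol and SAP.

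- **Power Analysis** gives the inputs, "With a power of 80%, a type I error rate (alpha) of 0.05, and a two-tailed t test", and concludes that "60 patients would have been needed in each group to detect a difference of at least 0.16 SD between the light and control groups". As background it cites a study of satisfaction with pain relief on a 1–5 scale, with ratings of 2.0 (± 0.37) under PCA and 3.0 (± 0.24) under control. It does not show how 0.16 follows from these figures, and it does not label the ± values as SDs.
- **Recruitment and Randomization** says "Recruitment continued until each group included 60 completed participants". Completion is defined to include assessment of the primary outcome.
- **Primary Outcome** defines the endpoint as the patient's "response to a single question, focused specifically on satisfaction with pain management", scored 0 to 10. No SD for this item appears anywhere.
- **Statistical Analysis** says that comparisons between the intervention and control groups "were conducted using a Mann-Whitney test", which is not the test used for sizing.

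**The concern.** A difference expressed in SD units needs no further input: sample size, alpha, sidedness and power fix it. An effect of 0.16 SD is very small, and 60 per group is far below what a two-arm comparison needs to detect it.

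This is the only sizing statement in the plan, and it concerns the primary outcome. Taken at face value, it says the trial had a good chance of finding even a very small difference in satisfaction. A reader who accepts that would take a non-significant result as strong evidence that the light cue makes no difference to satisfaction, when the trial could leave open differences well above 0.16 SD.

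**Working it through.** **Inputs.** n = 60 per group, 1:1, completed participants (Power Analysis; Recruitment and Randomization). Two-sided alpha 0.05, power 80%, t test, stated difference d = 0.16 SD (Power Analysis). Normal quantiles: 1.960 and 0.842, sum 2.802.

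**1. Attempt to reproduce 60 per group at 0.16 SD.**

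n per group = 2 × (1.960 + 0.842)² / d² = 2 × 7.849 / 0.0256 = 613.2, so 614. The exact noncentral t calculation gives 614.2, so 615. The stated 60 is not reproduced.

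**2. Power at 0.16 SD with 60 per group.**

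d × √(n/2) = 0.16 × √30 = 0.876. Power ≈ Φ(0.876 − 1.960) = Φ(−1.084) = 13.9%. Noncentral t: 14.0%.

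**3. Detectable difference with 60 per group.**

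2.802 × √(2/60) = 2.802 × 0.1826 = 0.511 SD. Noncentral t: 0.516 SD. Ratio to the stated value: 0.5157 / 0.16 = 3.22.

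**4. Other designs at 0.16 SD.**

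| Variant | Result |
|---|---|
| One-sided two-sample test | 484 per group needed; power 22% at 60 |
| One-sample or paired, n = 60 | power 23% |
| One-sample or paired, n = 120 | power 41% |

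None gives 60 per group or 80%.

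**5. Could 0.16 be raw points on the cited 1–5 scale?** Reading the ± values as SDs (an assumption):

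- Pooled SD = √((0.37² + 0.24²)/2) = √0.09725 = 0.312.
- d = 0.16 / 0.312 = 0.513, so n = 60 per group (normal) or 61 (t). Power at 60 is 80.2% (normal) or 79.6% (t).
- In reverse, 0.5157 × 0.3118 = 0.161 points.

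This reproduces the stated sample size. Using one arm's SD for both arms does not: 0.37 needs 85 per group and 0.24 needs 37 (t). The cited difference itself does not lead to 0.16 either, since 1.0 / 0.312 is 3.2 SD.

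**6. What 0.516 SD means on the 0–10 item.** The SD is not given, so a range is assumed:

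| Assumed SD | 0.516 SD in points | 0.16 SD in points |
|---|---|---|
| 1 | 0.52 | 0.16 |
| 2 | 1.03 | 0.32 |
| 3 | 1.55 | 0.48 |

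**7. The planned Mann-Whitney test.** With near-normal data its relative efficiency is 3/π = 0.955, so the effective n is 60 × 0.955 = 57.3 per group and the detectable difference is 0.528 SD. At the lower efficiency bound of 0.864 it is 0.556 SD. Simulations of normal scores rounded and capped to 0–10, with 1% to 58% of scores at 10 in the higher-scoring arm, reached about 80% power at 0.51 to 0.53 SD, measured in the SD of the observed scores. These shapes are assumed and others could differ, but none of these figures is near 0.16.

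**8. Precision.** The 95% confidence interval for a mean difference has half-width t(0.975, 118) × √(2/60) = 1.980 × 0.1826 = 0.36 SD. An observed difference of exactly zero would still be compatible with true differences of 0.36 SD, which is 2.3 times 0.16 SD.

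**The case against.** The strongest reply is that this is a slip of unit and not a failed calculation. Step 5 shows that the plan's own cited figures yield 60 per group once 0.16 is read as points on the 1–5 scale, and the shortfall factor of 3.22 is almost exactly 1/0.312 = 3.21, as such a slip would produce. Pooling the two SDs is also the standard choice, so the failure of the single-arm SDs counts for little. That stands as a likely explanation, and it means 60 per group should not be called miscalculated. It remains an inference, because the plan does not say how 0.16 arose; a miscopied 0.516 is also possible, though only the shared digits suggest it. Neither account makes the sentence correct. It says SD, and a raw difference on a 1–5 scale does not describe what can be detected on a 0–10 item of unknown SD.

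A second reply is that enrolment is reported as complete, no equivalence aim is stated for satisfaction, and sample size, alpha, test and analysis set are unaffected. That is true and limits the consequences to interpretation. It is not a reason to leave a wrong figure in the only sizing statement.

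A third reply is that conversions to points on assumed SDs, and the Mann-Whitney figure, were never part of the a priori calculation. That is fair: they should be presented as later additions and not as the original planning record.

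**Conclusion.** The concern holds. Under the plan's own alpha, power, test and sample size, the detectable difference is about 0.52 SD. The stated 0.16 SD is too small by a factor of about 3.2, the power for it is about 14%, and it would need about 615 per group. These figures rest only on inputs in the plan and on the standard two-sample t calculation.

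The raw-points explanation rests on reading the ± values as SDs. The point equivalents rest on assumed SDs of 1 to 3. The Mann-Whitney figure of 0.53 SD assumes near-normal data.

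The error misreports what the primary comparison can detect. It does not show that 60 per group was wrongly derived.

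**What to change.** Correct the sentence in the Power Analysis section, marked as a dated correction, with the sample size unchanged. Suggested text:

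> With 60 per group, two-sided alpha 0.05 and 80% power, a t test detects a difference of about 0.52 SD on the 0–10 satisfaction item.

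A useful addition, labelled as not part of the a priori calculation: this is about 0.5, 1.0 or 1.5 points if the SD is 1, 2 or 3 (assumed), and the planned Mann-Whitney test detects about 0.53 SD if the data are near normal, which may change with skew and ties.

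State where 0.16 came from, including its scale and the SD used, or delete it.

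Report a 95% confidence interval for the satisfaction difference, saying whether it is for a mean difference or for the shift estimate that accompanies the Mann-Whitney test. Do not interpret a non-significant result as evidence against differences near 0.16 SD.

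The cost is one corrected sentence and one reporting line. The stated detectable difference becomes less favourable. No patients are added and the test does not change.

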Alaris™ PCA pumps were used for all patients. The PCA profile (i.e. configuration of the light cue operation) for both groups was set up by a nurse in the post-anesthesia care unit (PACU). The starting opioid dose is standardized, and was set up by the PACU nurse. For the control group, the PCA pump was used according to the hospital's standard operating procedures: The PCA emitted a "beep" with every button press, and the status of the green light on the button never changed (i.e., it remained continually lit). For the light group, the PCA pump was configured so that the PCA button only emitted a "beep" when a button press resulted in successful opioid delivery. The green light on the button flashed during opioid delivery, was darkened immediately after delivery and was illuminated at the end of the lockout period, indicating a dose was ready to be delivered. Treatment of side effects was determined by the floor nurse who was not a member of the study team. To ensure consistent messaging, patients and parents in both groups were given scripted instructions regarding PCA use. The patient and guardian were also given a printed copy of the instructions prior to surgery.

PCA monitoring and Pain assessments

Either morphine or hydromorphone (converted to morphine equivalents) was administered using PCA for both groups as prescribed by the anesthesia service. Using morphine equivalents, our standardized PCA orders are as follows: 20 mcg/kg for the PCA dose and basal (if used), 8 minute lockout, and a 120 mcg/kg hourly maximum.

Patients had continuous pulse oximetry. Pain and sedation scores were recorded every 2 hours for the first 24 hours, with a minimum of every 4 hours thereafter. PCA use, including injections (i.e. button presses resulting in delivered doses) and attempts (i.e. button presses during the lockout period), were documented hourly by a nurse who was not a member of the study team. If for some reason the nurse was unable to document the hourly number of

injections and attempts (e.g. busy with another patient), the following hour's data would reflect the previous 2 hours' worth of attempts and injections.

Data collection terminated when the PCA was discontinued, or up to 60 hours post-surgery, whichever came first. The study period was defined as beginning when the patient arrived in the Post-Anesthesia Care Unit (PACU) through Post-Operative Day (POD) 2.

Measures

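### Listwise deletion under MCAR does not suit data that end when PCA is discontinued: later-day secondary comparisons can be biased, and an on-PCA rate misses any saving from earlier stopping

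*Combined protocol and SAP*

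**What the plan says.** **Missing-data rule.** The Statistical Analysis section compares the two arms, and the two age groups, by tests that "were conducted using a Mann-Whitney test". The next sentence reads: "Missing data were treated using listwise deletion, and assumed to be missing completely at random".

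**When observation ends.** Under PCA monitoring and Pain assessments: "Data collection terminated when the PCA was discontinued, or up to 60 hours post-surgery, whichever came first". Under Pain intensity, scores run from leaving the PACU "until discontinuation of the PCA or through POD 2 (whichever came first").

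**The multivariable models.** These have two dependent variables: "1) opioid consumption over time and, 2) injections:attempts ratio over time". They are fitted by maximum likelihood, and the plan adds: "The mixed model with random effects allows for missing data, under the assumption that data were missing at random". Pain enters only as a candidate covariate. State anxiety does not appear in them.

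**The opioid measure.** "Total opioid consumed via PCA was calculated from all opioid delivered via the basal rate and via injections", and it is expressed in mg/kg/hr. The documents do not say whether the hours after PCA stops count as missing, as zero, or not at all. They give no numbers, times or reasons for discontinuation, and they plan no sensitivity analysis for missing data.

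**The concern.** MCAR requires that whether a later value is observed has nothing to do with the patient's pain or opioid use. Here the protocol itself ends observation at discontinuation of PCA, which happens after randomisation and is plausibly related to both. The plan offers nothing in support of MCAR.

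Two things are at stake, both among the secondary outcomes.

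- **Selection.** An unadjusted later-day comparison, where one is made, would contrast the children still on PCA in one arm with those still on PCA in the other. If stopping depends on need, these are selected subsets. If the cue also changes how soon children stop, they are selected differently by arm.
- **What the rate can show.** PCA opioid after PCA stops is known to be zero. A rate taken over time on PCA ignores this, so a saving that arises through earlier stopping does not appear in it.

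**Working it through.** The plan gives no figure on this point to reproduce. The only input below that comes from the documents is 60 per arm and the 24 h and 60 h limits. Everything else is an assumption, so ranges are shown.

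**A. A true effect on need, seen only in those still on PCA**

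Assumptions: need on two consecutive days is standard normal within arm with correlation 0.7. The true light-minus-control effect is δ = -0.3 SD on both days. A patient stays on PCA if day-1 need exceeds a threshold. If a proportion k stays, with cut-off t = Φ⁻¹(1-k), the mean standardised need of those who stay is φ(t)/k. The expected complete-case difference on day 2 is therefore

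δ + 0.7 × [φ(t_light)/k_light - φ(t_control)/k_control].

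For 70% of controls and 40% of the light arm still on PCA:

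- control: φ(-0.524)/0.70 = 0.348/0.70 = 0.497
- light: φ(0.253)/0.40 = 0.386/0.40 = 0.966
- difference: -0.3 + 0.7 × (0.966 - 0.497) = -0.3 + 0.328 = +0.03

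Simulation at 60 per arm agrees. The likelihood column uses the day-1 value and assumes MAR.

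| Still on PCA, control / light | Complete-case mean | Wrong sign | Likelihood under MAR |
|---|---|---|---|
| Common threshold, controls 90% | -0.23 | 10% | -0.29 |
| Common threshold, controls 70% | -0.18 | 17% | -0.30 |
| Common threshold, controls 50% | -0.17 | 23% | -0.30 |
| 90% / 80% | -0.19 | 14% | -0.30 |
| 70% / 50% | -0.09 | 34% | -0.30 |
| 70% / 40% | +0.02 | 55% | -0.30 |
| 60% / 30% | +0.06 | 60% | -0.30 |

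The complete-case estimate is biased in every row. Its mean reverses only in the last two. At 70% / 40% the shift is 0.328 whatever δ is: a true -0.2 becomes +0.13 and a true -0.5 becomes -0.17.

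If stopping depends on the unrecorded current need instead, the factor 0.7 becomes 1. At 70% / 40% the complete-case mean is then -0.3 + 0.469 = +0.17, and the MAR estimate is +0.03. MAR does not rescue that case.

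**B. An effect on duration only**

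Assumptions: need is log-normal with median 30 mcg/kg/h and log-SD 0.5. Stop time averages 44 h at median need, rises 12 h per SD of log need, has residual SD 8 h, and is limited to 24-60 h. POD 2 is taken as hours 36-60.

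- Mean need in all patients: 30 × exp(0.5²/2) = 34.0 mcg/kg/h.
- Without a cue effect, 71% are on PCA after hour 36. Their mean is 39.9, and 39.9/34.0 = 1.17, or 17% above that of all patients. The 60 h total averages 1.64 mg/kg.

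Now let the light arm stop 6 h earlier with its rate on PCA unchanged. About 55% of that arm is still on PCA after hour 36.

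- On-PCA rate, POD 2: light about 3.6 mcg/kg/h higher (3.6/39.9 = 9%), standard error about 4.2.
- Total PCA opioid to 60 h: light about 0.16 mg/kg lower (0.16/1.64 = 10%), standard error about 0.22.
- POD 2 rate with zero after stopping: light about 5.0 mcg/kg/h lower.

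Varying the inputs:

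| Change from the 6 h case | On-PCA rate, mcg/kg/h | 60 h total, mg/kg |
|---|---|---|
| No arm difference in stop time | 0 | 0 |
| 3 h earlier | about +1.7 | -0.08 |
| Need link 4 h per SD | +2.6 | -0.20 |
| Need unrelated to stopping | about 0 | -0.20 |
| Plus a true 5% rate reduction | +1.4 | not tabulated |
| Plus a true 10% rate reduction | -0.8 | not tabulated |

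Even where selection does no harm (need unrelated to stopping), the on-PCA rate shows nothing of the 0.20 mg/kg saving.

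**The case against.** The strongest reply is that much of this is already handled. Opioid consumption and the injections:attempts ratio have a likelihood model under MAR, which in part A recovers the true effect whenever stopping follows recorded values. Using different missing-data assumptions for simple tests and for a likelihood model is not in itself a contradiction. The plan does not spell out day-by-day Mann-Whitney tests; collection by POD only implies them. If the mg/kg/hr figure is one rate per patient over that patient's PCA time, early stopping deletes nobody from it. All of this stands, and it confines the point to unadjusted secondary comparisons where they are made, to pain and anxiety as outcomes, and to what a rate can show.

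A reader might infer four stronger things that the documents do not support.

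- **That later-day data come only from the children in greatest need.** No reasons for stopping are given. Side effects or routine practice would fit the text as well.
- **That the comparisons will have the wrong sign.** In part A this needs strongly arm-dependent stopping. In part B the opposite signs belong to two different quantities, a rate and a total, under wholly assumed inputs, and each difference is below one standard error at 60 per arm.
- **That the plan codes known zeros as missing.** It does not say how hours after PCA are treated.
- **That the primary result is compromised.** Satisfaction is one rating, given within 24 hours of the end of the study period, and PCA stopping does not cut it off. No case for imputing it follows from this argument.

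For anxiety there is a further reservation. The cut-off rests on the general rule that data collection ends with PCA; the State Anxiety section simply schedules one assessment a day on POD 1 and POD 2.

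**Conclusion.** The point holds for secondary outcomes. MCAR with listwise deletion is hard to defend when the protocol ends observation at an event plausibly related to the outcomes. Unadjusted later-day comparisons can be biased. Under a common stopping threshold, a true -0.3 SD effect is attenuated to between -0.17 and -0.23. Reversal is possible if discontinuation differs by arm, at about 70% against 40% still on PCA for an effect of that size. Separately, a 6 h earlier stop would lower total PCA opioid by about 10% under the part B assumptions without appearing as a saving in an on-PCA rate. None of these sizes can be tied to the trial, because the documents report no discontinuation figures. This should be changed, but it does not call the primary analysis into question.

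**What to change.** 1. Drop the MCAR/listwise rule for repeated secondary outcomes. Analyse pain and anxiety as outcomes with a likelihood-based mixed model of the type already planned for opioid consumption, using all available PODs under MAR. State that MAR does not cover stopping driven by unrecorded need.
2. Beside the mg/kg/hr rate, report total PCA opioid in mg/kg from PACU arrival to 60 h, counting zero after PCA stops and labelled as PCA opioid only. Compare time to PCA discontinuation by arm, and give the number still on PCA on each POD.

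The cost is SAP wording and a few extra secondary analyses; the hourly pump records should supply the data. The drawback is that the total leaves out opioid given by other routes. A child who stops PCA early and moves to another opioid would look like a saving, so the total must be read next to the rate.

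### Age group is not randomised, yet its effect is examined without surgical procedure or sex, so the age estimate can be confounded by the mix of operations

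*Combined protocol and SAP*

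**What the plan says.** The Statistical Analysis section makes age group a target of inference beside the randomised arm. The mixed models are "used to examine the effect of the intervention group and age group on two dependent variables (DV"), the two variables being opioid consumption and the injections:attempts ratio, both over time. The same section states that comparisons "between age groups [children (≤ 12 years) and adolescents (13-17 years)] were conducted using a Mann-Whitney test".

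The candidate terms are listed: "The independent covariates (IV) considered were pain scores, methadone use and the interaction between methadone use and intervention group, age group, intervention group", and lastly the interaction of age group with intervention group. The selection rule follows: "A backward model selection procedure was used, with a p-value <0.05 as a criterion to keep the variable in the multivariable model". Significance is set in one sentence: "A two-sided p-value <0.05 was used to define what was considered significant".

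Under Recruitment and Randomization, "participants were randomized into either the control group or the experimental" light group, and allocation was "stratified by gender and surgical procedure (orthopedic, abdominal, or thoracic) in blocks of 4". Sex also appears among the collected data: "Demographics (age, sex, race and ethnicity) and anthropometrics (height, weight, and BMI percentile) were extracted from the EHR".

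Nowhere does the document adjust an age comparison for procedure or sex, or explain why they are left out.

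**The concern.** Randomisation protects the light-versus-control contrast. It gives no protection to a contrast between children and adolescents, because age is a patient characteristic. The trial pools orthopedic, abdominal and thoracic surgery over ages 7 to 17. If older patients have a different mix of operations, and the operations differ in opioid need, the age term takes up the procedure difference. The design treated procedure as important enough to stratify on, but the analysis of a non-randomised factor leaves it out.

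At stake is the interpretation of any age finding on opioid use, pump use or satisfaction. A difference due partly or entirely to the type of operation would be described as an effect of age. The concern is bias in the age estimate, not precision of the arm estimate.

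**Working it through.** **Step 1: can procedure or sex enter the model?** The candidate list has six terms: pain scores, methadone, methadone × arm, age group, arm, and age group × arm. Neither procedure nor sex is among them. Backward selection only removes terms, so neither can enter. The Mann-Whitney test has no covariates at all.

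**Step 2: are the data available?** Stratified allocation needs procedure and sex to be known for each randomised patient. Sex is also taken from the health record.

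**Step 3: size for the unadjusted comparison.** The plan states no figure to reproduce. It gives 60 completed participants per randomised arm (120 in total), but no age-group sizes, procedure mix by age or procedure effect. Every input below is therefore an assumption, except the two-sided 0.05 level:

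- 60 patients per age group and no true age effect
- orthopedic share *p*₁ = 70–80% in adolescents and *p*₂ = 40–50% in children
- procedure effect *e* = 0.5–1.0, in units of the SD within procedure

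Formulas:

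- spurious age difference: *d* = (*p*₁ − *p*₂) × *e*
- total SD: *s* = √(1 + *e*² × [*p*₁(1 − *p*₁) + *p*₂(1 − *p*₂)]/2)
- standard error: SE = *s* × √(2/60)
- approximate rejection rate: Φ(*d*/SE − 1.96) + Φ(−*d*/SE − 1.96)

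| Orthopedic share, adolescents vs children | *e* | *d* (SD) | *s* | SE | *d*/SE | Rejection rate |
|---|---|---|---|---|---|---|
| 70% vs 50% | 0.5 | 0.20 × 0.5 = 0.10 | 1.028 | 0.188 | 0.53 | 8.3% |
| 80% vs 50% | 1.0 | 0.30 × 1.0 = 0.30 | 1.098 | 0.200 | 1.50 | 32.2% |
| 80% vs 40% | 1.0 | 0.40 × 1.0 = 0.40 | 1.095 | 0.200 | 2.00 | 51.6% |
| equal | any | 0 | – | – | 0 | 5% |

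The formula is for a two-sample comparison of means. Simulating the Mann-Whitney test itself (4,000 data sets per scenario, repeated independently) gave 8–9% in the first row, about 32% in the second and 50–52% in the third. With procedure in a linear model, the age coefficient was about 0 and the rejection rate 4–6% throughout.

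**Step 4: do pain scores and methadone remove the bias?** A separate simulation used 120 patients, one outcome per patient, 1,500 runs per scenario and no true age effect. The linear model contained age, arm, pain and methadone. Assumed procedure effects were 0.8 (orthopedic), 0.4 (thoracic) and 0 (abdominal) residual SD. The thoracic share was 20% in both age groups, so the direct procedure contribution is the gap in orthopedic share × 0.8.

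| Orthopedic share, children vs adolescents | Direct procedure contribution | False age effect without procedure and sex | Type I error without | Type I error with both |
|---|---|---|---|---|
| 50% vs 50% | 0 | about 0 | 5–6% | 5–6% |
| 40% vs 60% | 0.20 × 0.8 = 0.16 | 0.13–0.15 SD | about 11% | 4–6% |
| 20% vs 70% | 0.50 × 0.8 = 0.40 | 0.33–0.39 SD | 37–50% | about 5% |

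Under these assumptions the two covariates take up part of the procedure difference and leave the rest. This is a single-outcome model, not the planned repeated-measures model. It shows that bias can remain, and gives no rates for the planned analysis.

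**The case against.** Several points on the other side stand.

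- **No bias is demonstrated.** Every input on mix and effect is assumed, and with equal mix the bias is zero. A reader might infer that the trial's age effect is only the mix of operations. The documents do not support that: they report no age estimate and no procedure distribution by age.
- **The Mann-Whitney comparison may be descriptive.** It asks whether distributions differ between age groups. If the mix differs, rejecting is the right answer to that question, and calling it a false positive is fair only under a causal reading. The plan calls these tests comparisons. It uses the word effect for the mixed models, and there the objection does not apply.
- **The rates in step 3 do not describe the mixed models.** Pain scores and methadone may carry part of the procedure difference there. However, pain scores are post-operative and do not stand in for procedure.
- **The case for sex is not quantified.** Nothing here links sex to both age group and outcome. It is included because it is a stratification factor.
- **Age is not the main question.** The primary outcome is satisfaction, and the sample size compares the arms. A reader might infer that the arm result is also biased. It is not: arms are randomised within procedure and sex. The age × arm term is less exposed than the age main effect, though it could reflect a treatment effect that varies by procedure.

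Stratified allocation does not answer the concern, because it balances the arms and not the age groups.

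**Conclusion.** The concern holds as a possibility that the plan leaves open. Age group is a stated effect of interest and is not randomised. It is analysed without two variables that the trial holds and stratified on. If procedure mix differs by age and procedures differ in opioid need, the estimated age effect is confounded.

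Under the assumptions in step 3, the unadjusted difference is 0.10–0.40 SD and the Mann-Whitney test rejects in about 9–51% of trials, against about 5% with procedure in the model. These rates belong to the Mann-Whitney test only. The bias in the mixed models may be smaller, and its size cannot be derived from the documents. This should be corrected, but it does not threaten the primary comparison of the arms.

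**What to change.** 1. In both mixed models, add surgical procedure (three levels) and sex as fixed terms exempt from backward selection. Base age conclusions on opioid consumption and the injections:attempts ratio on the adjusted contrast.
2. The mixed models do not cover satisfaction or the other outcomes compared by age. For these, use a rank test stratified by procedure and sex (van Elteren) or a proportional-odds model with both terms. Otherwise keep the unadjusted Mann-Whitney test and label its result descriptive.
3. Tabulate procedure and sex by age group, so that readers can see whether the mix differs.
4. Report age findings as associations, not effects.

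The cost is about three degrees of freedom (two for procedure, one for sex). The text already describes a term being dropped from a fitted model, so the models must also be re-run. No new data are needed.
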